- ⁷³ lorcaserin (Belviq®) was associated with euphoria (0.2% vs < 0.1% for placebo) and is contraindicated in
- 74 patient's receiving serotonergic medications (and many psychotropics enhance serotonin function) (45). 75 Phenermine/topiramate combination (Qsymia®), at the highest approved dose, was associated with
- insomnia (11.1% vs 5.8% for placebo), depression/mood problems (7.6% vs 3.4% for placebo), and
 anxiety (7.9% vs 2.6% for placebo) (46). Additionally, one of the components of Qsymia®, topiramate, is 78
 associated with suicidality. Bupropion/naltrexone combination (Contrave®), at the highest recommended 79
 dose, was associated insomnia (9.2% vs 5.9% for placebo), anxiety (4.2% vs 2.8% for placebo), and
- irritability (2.6% vs 1.8% for placebo) (47). Moreover, there are reports of components of these latter
- medications (e.g., phentermine and bupropion) causing severe adverse psychiatric events, such as mania
- and psychosis (48-52). Taken together, these findings suggest that liraglutide 3.0 mg sc injection may be
- the least likely of these weight management medications to exacerbate psychiatric symptoms in people 84
- with BP. Indeed, GLP-1 analogues have been reported to produce enhanced well-being in patients with diabetes (53).
- 86
- Taken together these data support the hypothesis that liraglutide 3.0 mg sc injection will reduce body
 weight and improve metabolic variables in obese or overweight patients with BP without worsening 89
 psychiatric symptoms. We predict that liraglutide 3.0 mg sc injection will display greater efficacy as
- ⁹⁰ compared to placebo in decreasing body weight in patients with BP who are obese or overweight. To
- 91 prove this hypothesis, we will conduct a single-center, randomized, placebo-controlled, double-blind,
- parallel-group, 2-arm clinical trial of liraglutide 3.0 mg sc injection in 60 obese or overweight outpatients

with stable BP. We have chosen BP rather than another SMI because it is the most common SMI (more

- 94 common than schizophrenia or schizoaffective disorder) and has a particularly strong association with 95 obesity.
- 96

97 SPECIFIC OBJECTIVES:

98 **Primary Objective:**

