99 The primary objective of this study is to evaluate the efficacy of liraglutide 3.0 mg sc injection (in 100 combination with a reduced calorie diet and increased physical activity) compared with placebo for 101 reducing body weight in obese or overweight adults with stable BP, as measured by percent change in 102 body weight.

103

104 Secondary Objectives:

105 Secondary objectives are:

105	Secondary objectives	
106	- To ev	aluate the efficacy of liraglutide 3.0 mg sc injection as measured by:
107	-	Proportion of participants who have $a \ge 5\%$ loss in body weight
108	-	Body weight (kg)
109	-	BMI
110	-	Waist circumference
111	-	Fasting lipids
112	-	Fasting glucose
113	-	HgA1 _c levels
114	-	Three-Factor Eating Questionnaire (TFEQ) (54)
115	-	Binge Eating Scale (BES) (55)
116	- To ev	aluate the safety and tolerability of liraglutide 3.0 mg sc injection, using:
117	-	Mental status examinations
118	-	Young Mania Rating Scale (YMRS) (56)
119	-	Montgomery Asberg Depression Rating Scale (MADRS) (57)
120	-	Clinical Global Impressive Scale for modified Bipolar Disorder (CGI-BP) (58)
121	-	Physical examinations
122	-	Vital signs
123	-	12-lead electrocardiograms (ECG)
124	-	Clinical laboratory tests
125	-	Adverse event reports
126	-	Columbia-Suicide Severity Rating Scale (C-SSRS) (59)
127		
128	RESEARCH DESIG	GN AND METHODS
129		
130	Study hypothesis (es	s):
131		question is whether liraglutide 3.0 mg sc injection is efficacious for reducing body
132		verweight patients with BP. We hypothesize that liraglutide 3.0 mg sc injection will
133		e, and well tolerated treatment for weight loss in obese or overweight patients with
134		et that liraglutide 3.0 mg sc injection will display greater efficacy as compared to 135
	1 1 1 1 1	

- placebo in decreasing body weight in patients with BP who are overweight or obese without increasing
- 136 psychiatric adverse events. We also predict that liraglutide 3.0 mg sc injection will produce a greater

- percentage of patients who lose \geq 5% of baseline body weight, and improve BMI, waist circumference, 137
- fasting lipid and glucose levels, HgA1c levels, and measures of eating psychopathology. 138
- 139

140 **Endpoints:**

- The primary endpoint will be the percent change in body weight from Baseline (Week 0) to week 141
- 40/Early Termination (ET) (see Table 1 for a schedule of assessments). Secondary endpoints will include 142

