- proportion of participants who lose \geq 5% of baseline body weight, and change from baseline in body 143
- 144 weight (kg), BMI, waist circumference, and metabolic variables (fasting lipids and glucose, and HgA1c
- levels). Exploratory secondary endpoints will be change from baseline in eating psychopathology, 145
- 146 assessed with the Three Factor Eating Questionnaire (TFEQ) (54) and Binge Eating Scale (BES) (55). 147 Safety endpoints assessed at each study visit will be mental status examination, clinically-administered 148 scales that assess psychopathology (CGI-BP scale [both Severity and Improvement subscales], YMRS, 149 MADRS, and CSSRS), vital signs, and adverse events determined by clinical interview. Laboratory tests
- and 12-lead electrocardiograms (ECGs) will be obtained at Screening, week 8, week 16/ET, and week 151 150 40/ET. Compliance will be assessed at each visit with inspection of returned multi-dose pens. Potential
- interactions between liraglutide and psychiatric medications will be monitored and recorded on the 152
- Potential Drug Interaction form (see p. 28). 153
- 154

Study type: 155

- This is a single-center, randomized, placebo-controlled, double-blind, two-arm, parallel-group, fixed-dose 156
- efficacy and safety study with 3 phases: a 3-27 day Screening period; a 40-week randomized, double-157
- blind Treatment period (4 weeks of dose titration and 36 weeks of dose maintenance); and a 1-week 159 158 Follow-up (drug discontinuation) period. The purpose of the 40-week Blinded Treatment phase is to
- establish the efficacy of liraglutide 3.0 mg sc injection for weight loss in obese patients with stable BP. 160 161

Study population: 162

163 We expect to screen about 90 subjects in order to randomize 60 subjects in a 1:1 ratio to drug or placebo.

- Patients will be recruited from the Lindner Center of HOPE, Mason, OH, a University of Cincinnati 164
- College of Medicine Affiliate. Patients will be recruited by clinician referral and advertisement. 165
- 166
- Participants will include 60 outpatients with a DSM-IV (60) diagnosis of BP that is stable, who are obese 167
- or overweight with at least one weight-related comorbidity, and who have been receiving a stable 168
- psychotropic regimen for the past three months. The weight-related comorbidities to be included will be 169
- hypertension, type 2 diabetes, and dyslipidemia. Allowed psychotropic medications for BP will include 170

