- mood stabilizers (lithium, valproate, and lamotrigine), antipsychotics (asenapine, aripiprazole, 171
- cariprazine, chlorpromazine, clozapine, haloperidol, loxapine, olanzapine, paliperidone, perphenazine, 172
- quetiapine, resperidone, thiothixene, trifluoperazine, or ziprasidone), antidepressants, and anxiolytics 173
- (benzodiazepines, gabapentin or pregabalin, and buspirone). Stable BP will be operationally defined as a 174
- CGI-BP-Severity score of 1through 3 (1= normal, not at all; 2= borderline mentally ill; 3=mildly ill); a 176 175 YMRS score ≤ 12 ; a MADRS score ≤ 19 , and the absence of clinically significant suicidality and
- psychosis. Participants must be 18 through 65 years of age, be able to provide informed consent, and if 177
- female, be postmenopausal, surgically incapable of childbearing, or practicing a medically acceptable 178 method(s) of contraception (e.g., hormonal method, intrauterine device) for at least 1 month prior to study 179
- entry and throughout the study. Exclusion criteria include subjects with a lifetime DSM-IV Axis I
- 180
- 181 diagnosis of dementia, a psychotic or depressive disorder, or a sub

- stance use disorder within the past three months; those with clinically significant psychotic features or 183 suicidal ideation; those with serious or unstable general medical illnesses; those with a personal or family
- 184 history of medullary thyroid cancer or Multiple Endocrine Neoplasia syndrome type 2; those who are
- allergic to or who have demonstrated hypersensitivity to liraglutide 3.0 mg sc injection or any of its
- components; and females who are pregnant, nursing, or intend to become pregnant. Specific entry criteriaare listed below.
- 188

189 Inclusion Criteria: Criteria for entering this study will include all of the following:

- 190 1. Men and women, ages of 18-65 years, inclusive.
- 191 2. Participants will have a DSM-IV bipolar disorder that is clinically stable.
- Participants will have received a stable major psychotropic drug regimen (except for minor dosage adjustments) for at least 3 months prior study entry. Major psychotropic drugs are antipsychotics, mood stabilizers, and antidepressants. Subjects may have had changes in adjunctive benzodiazepines and hypnotic agents.
- 4. Participants will be obese (defined as a $BMI \ge 30 \text{ mg/kg}^2$) or overweight (defined as $BMI \ge 27$ kg/m²) with at least one weight-related comorbidity, such as hypertension, type 2 diabetes, or dyslipidemia.

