259 Participants may withdraw at will from the study at any time. Participants will be withdrawn in the event of pregnancy or intention to become pregnant. Additionally, participants will be discontinued if they 260 261 display: clinically significant suicidality, defined as a YES to item 1 of the C-SSRS or a C-SSRS-defined suicide attempt; a YMRS score >12 (indicating at least moderately ill manic symptoms); a MADRS score 262 >19 (indicating at least moderately severe depressive symptoms); a CGI-I-BP-Severity score of much or 263 very much worsened; or clinically significant suicidal ideation or psychotic symptoms on mental status 265 264

- examination. In the absence of the above, participants will be terminated at the treating psychiatrist's discretion in response to symptoms of sufficient severity that a new psychiatric medication needs to be 267 266
- added (dosage changes in ongoing psychotropics will be permitted). The Investigator may also withdraw participants for lack of compliance with study procedures if she or the research team has any concerns for 268
- the participant's safety. Upon termination for any of these reasons, patients will receive care judged 269
- appropriate by the treating investigators including, if needed, referral for emergency care. 270
- 271
- 272 Participant compliance with dosing requirements will be monitored with pen inspection. Participants
- displaying non-compliant behaviors with study medication administration and accountability (such as 273

- taking more medication than prescribed, losing pens, or failure to return pens to clinic) will be re-
- educated. .
- 276

277 Subject Replacement:

278 Subjects will not be replaced if they withdraw or become ineligible at any time after the Baseline visit.

279

280 **Rational for study population:**

Approximately half of persons with BP are obese, yet no medication is regularly used (or indicated) for

- weight loss in this population, signifying a large unmet medical need. Data showing that a weight loss
- drug is beneficial in obese persons with BP would be a significant advancement to the medical field. 284
 Visit Procedures:

286 During Screening, patients will be evaluated for eligibility. During the 40-week Blinded Treatment

- period, patients will be scheduled for weekly visits for the first 4 weeks of treatment (dose titration, Visit
- 0 through Visit 4), every other week for 12 weeks (dose maintenance, Visits 5 through 10), and then every

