479 Regarding adverse event evaluation, participants will be asked if they have experienced any unusual or unwanted symptoms at each visit (none will be suggested, and adverse experiences will be classified and 480 grouped by body system, using a coding system based on the National Adverse Drug Reaction Directory 481 [COSTART]). Adverse events will be recorded on the adverse event form. All adverse events will be 482 evaluated as potential drug interactions with those medications the subject is receiving for treatment of his 483 or her BP (mood stabilizers, antipsychotics, antidepressants, anxiolytics, and sedative-hypnotics) with the 484 drug interaction form. Potential drug interactions will be recorded on the drug interaction form. Other 485 486 safety evaluations, all done at Screening and Visits 16/ET, will be: physical examination; routine laboratory evaluations, including hematology, serum chemistry, and urinalysis; and an ECG. The 487 interpretation of ECG results will follow the categories "normal", "abnormal", "not clinically significant" 488 or "abnormal, clinically significant" and only "normal" and "abnormal, not clinically significant" results 489 490 will be allowed at Baseline. Urine pregnancy tests will be performed at every visit post Baseline. Abnormal clinical laboratory or physical exam results will be clinically evaluated to determine if 491 intervention is warranted.

492 493

494 **Other Assessments:**

The TFEQ is a reliable and validated self-report measure of three domains of eating behavior often 496 deranged in people with obesity: hunger, disinhibition over eating, and cognitive restraint over eating
(54). The BES is a valid and reliable self-report scale that assesses the presence and severity of binge eating symptoms (55).

499

Subject Compliance 500

- Subjects are instructed to bring their unused study medication and packaging to every visit. Subject 501
- compliance and drug accountability will be assessed by the investigator at every treatment phase visit by 502
- 503 individual pens inspection and entered on the drug accountability log. Compliance will be assessed at 504 each visit with inspection of returned multi-dose pens. Subjects taking 80-100% of prescribed study medication will be considered compliant. 505
- 506

507 STATISTICAL CONSIDERATIONS: 508

509 **Sample Size Calculation**

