- interaction. The statistical test for the interaction term will be the measure of a treatment effect. The 535 534 interaction term will test if the slopes of the regression lines for the liraglutide and placebo groups are 536 different. A group difference (Drug [week 40-week 0] – Placebo [week 40-week 0]) will be reported 537 which corresponds to the interaction term. For the primary outcome of percent change in body weight,
- only post-baseline data will be used in the LDA model and the difference between treatments at week 40 538
- will be reported. These mixed models will allow for random coefficients (intercept and time variable), as 539
- 540 well as an appropriate correlation structure for the error terms to account for within-subject
- correlation. The best model will be chosen using the Akaike Information Criterion-corrected 541
- (AICc). The distribution of the outcome measures will be checked for normality, and transformations will 542 be used when necessary. Also, a transformation on the time variable will be considered to optimize the 544 543
- assumed linear relationship.
- 545

- 546 Additionally, secondary endpoint analyses will be performed on all outcome measures. Using the last
- 547 observation carried forward (LOCF), baseline to endpoint change scores will be computed for each 548 measure and two-sample t-tests or Wilcoxon rank sum tests will be used to compare these changes 549 between the treatment groups.
- 550

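### The hypothesis of no psychiatric worsening rests on separate non-significance tests, and no endpoint counts the participants discontinued for psychiatric worsening

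*Combined protocol and SAP*

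**What the plan says.** **The aim.** The closing paragraph of the background expects liraglutide to "improve metabolic variables in obese or overweight patients with BP without worsening" psychiatric symptoms. Study hypothesis (es) predicts greater efficacy than "placebo in decreasing body weight in patients with BP who are overweight or obese without increasing" psychiatric adverse events. Safety and tolerability are a secondary objective.

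**Entry and exit.** Study population defines stable illness by, among other things, "YMRS score ≤ 12 ; a MADRS score ≤ 19". Withdrawal Criteria discontinues participants at "a YMRS score >12 (indicating at least moderately ill manic symptoms", at a MADRS score above 19, at a much or very much worsened CGI-BP rating, or for suicidality or psychotic symptoms. Termination is also at the psychiatrist's "discretion in response to symptoms of sufficient severity that a new psychiatric medication needs to be" added. Discontinued participants are not replaced.

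**What is measured.** Endpoints states: "Safety endpoints assessed at each study visit will be mental status examination, clinically-administered" scales (CGI-BP Severity and Improvement, YMRS, MADRS, C-SSRS), vital signs and adverse events. The scales are repeated at the early termination visit and at Visit 17, seven days later. A termination record is completed. Under Assessments for Safety, participants are asked about unusual or "unwanted symptoms at each visit (none will be suggested, and adverse experiences will be classified and" grouped by body system.

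**How it is compared.** Statistical Methods specifies a mixed model for the outcome measures and, with last observation carried forward, "baseline to endpoint change scores will be computed for each" measure, compared by t-test or Wilcoxon test. Testing is two-sided at p ≤ 0.05. Chi-square and Fisher tests are available for categorical outcomes, but no psychiatric categorical outcome is named.

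**The concern.** The YMRS and MADRS ceilings for entry are the thresholds for exit. If the rule is followed, everyone who reaches week 40 had YMRS ≤ 12 and MADRS ≤ 19 at every earlier visit. A participant who relapses contributes one score above the line, a rating seven days later, and nothing more. Relapse also takes several forms: a manic exit may leave MADRS unchanged, and a depressive exit may leave YMRS unchanged. Removal for psychiatric worsening, the event closest to the hypothesis, is recorded but is not an endpoint and has no planned comparison between arms.

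The trial could therefore report no significant difference on each scale and read this as support for its hypothesis. With these numbers the data might be compatible with a substantial excess of psychiatric exits on liraglutide. The background uses expected psychiatric tolerability to argue for this drug over other weight-loss agents, so the conclusion matters.

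**Working it through.** **1. The plan's own figure.** Sample Size Calculation gives 56 participants (28 per arm), two-sided 0.05, power 0.80 and a detectable effect of 0.76. A two-sample t-test with 28 per arm gives 0.762, so the figure reproduces. It concerns weight. No power, margin or precision is stated for psychiatric safety.

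**2. What a null result would show.** Suppose 3 of 28 in each arm are discontinued for psychiatric worsening.
- The proportion is 3/28 = 0.107. Its Wilson 95% limits are 0.037 and 0.272.
- Newcombe half-width = √[(0.107 − 0.037)² + (0.272 − 0.107)²] = √(0.0049 + 0.0272) = 0.179.
- The difference is 0, with a 95% interval of −17.9 to +17.9 percentage points.

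Equal counts would not exclude an excess of nearly 18 points.

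**3. How far an excess shifts the scale means.** The documents give no relapse rates or scale SDs, so everything here is assumed: exits of 10% on placebo and 30% on liraglutide; 50% depressive, 30% manic, 20% suicidality or psychosis; mean baseline MADRS about 8 and YMRS about 4; exit scores of MADRS 20–28 (middle 24) or YMRS 13–22 (middle 17.5).
- MADRS: 0.20 × 0.50 × (24 − 8) = 1.6 points.
- YMRS: 0.20 × 0.30 × (17.5 − 4) = 0.8 points.

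**4. Chance of detection.** These are simulations with 28 per arm, the crossing score kept and carried forward, and two-sided 0.05. Fisher figures are exact. For CGI-BP Severity, baseline is assumed to be 1–3 and the exit score 4–5.

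| Comparison | 10% vs 30% | 10% vs 40% |
|---|---|---|
| MADRS t-test | 14% | 26% |
| YMRS t-test | 10% | 16% |
| Either MADRS or YMRS | 23% | 39% |
| CGI-BP Severity, all exits move it | 36% | 62% |
| CGI-BP Severity, 60% of exits move it | 20% | 32% |
| Count of exits (Fisher) | 33% | 66% |

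A second simulation used different assumptions: 30 per arm and exits split evenly between mania and depression. At 10% vs 40% it gave 30% for YMRS, 24% for MADRS, 48% for either and 70% for the count. With no true difference, the either-scale rule was positive about 9% of the time and Fisher about 1%. The mixed model was not simulated.

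**5. Limits of the count itself.** With 30 per arm, Fisher detects 10% vs 20% about 10% of the time. By the pooled normal approximation, 80% power would need 199 per arm for 10% vs 20% and 62 per arm for 10% vs 30%.

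**The case against.** Four objections are fair.

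- **The event is not lost.** A reader might infer that removing participants at the threshold hides relapse from the scales. The documents do not support that. Final Treatment Phase Evaluation repeats every scale at early termination, and Statistical Methods carries the last value forward. This stands. What is lost is the later course and a single place where exits are added up.
- **Relapse is already an adverse event.** A reader might infer from the open question that relapses escape adverse event reporting. Adverse Event Reporting and Definitions covers any undesirable medical event, and every event meeting it must be collected. Endpoints adds that events are determined by clinical interview. This stands, so there is no need to turn every threshold crossing into an adverse event.
- **CGI-BP is a planned global measure.** It is not tied to one pole. If it moves at every exit, it detects an excess about as well as the count (36% vs 33%, and 62% vs 66%). This stands as stated; the advantage returns if only 60% of exits move it.
- **The count is noisy and the trial is small.** A YMRS change from 12 to 13 is a trigger, so measurement fluctuation is mixed with mood episodes, and the sample size limits any method. Both points stand. They argue for a breakdown by trigger and an interval, but not for leaving the exits uncounted.

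**Conclusion.** The concern holds as one of inference and reporting. The plan states a hypothesis of no psychiatric worsening, provides only separate difference tests without a margin, and has no endpoint for discontinuation due to psychiatric worsening. With 28 to 30 per arm, non-significance on individual scales cannot support no increase. The interval of about ±18 points at 3/28 in each arm shows the scale of the uncertainty; it needs only the assumed counts.

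The tempting stronger conclusion is that the planned measures would miss an excess that a count would catch. That is not established. The advantage is clear against MADRS or YMRS alone but largely disappears against CGI-BP if CGI-BP moves at every exit. All detection figures rest on assumed rates and score distributions, so only their direction should be relied on. The count would not make the trial adequately powered for psychiatric safety either. It would show openly what the trial can and cannot exclude, and should be prespecified because a tabulation chosen after unblinding would be discretionary.

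**What to change.** No change to the discontinuation rules is proposed.

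1. In Endpoints and Assessments for Safety, add a prespecified safety endpoint: the proportion of the safety population meeting any listed psychiatric trigger in Withdrawal Criteria by week 40 (C-SSRS, YMRS, MADRS, CGI-BP, or suicidality or psychosis on mental status examination), by arm, with time to first trigger.
2. Break it down by trigger so that marginal threshold crossings are visible.
3. In Statistical Methods, report the between-arm difference with its 95% interval. State that no increase is judged on that interval, and not on p > 0.05 for individual scales.
4. Tabulate removals for a new psychiatric medication separately. Withdrawal Criteria makes the need for one a ground for termination, while Visit Procedures permits adding antipsychotics, mood stabilizers and antidepressants. These passages must be reconciled before such removals can be counted consistently.
5. Leave adverse event recording to the existing definition.

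The cost is protocol and SAP wording and one table; the ratings are already taken at every visit. The downside is that the interval will be wide, so the safety statement will be less favourable than a report of no significant difference.
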